8.10 Accountability and Destruction of Sponsor-Supplied Clinical Trial Materials

The investigator or designee must ensure that the sponsor-supplied investigational vaccine and placebo are used in accordance with the approved protocol and are administered only to subjects enrolled in the trial. To document appropriate use of sponsor-supplied trial vaccine, the investigator must maintain records of all sponsor-supplied trial vaccine delivery to the site, site inventory, administration and use by each subject, and return to the sponsor or designee.

Upon receipt of sponsor-supplied trial vaccine, the investigator or designee must verify the contents of the shipments against the packing list. The verifier should ensure that the quantity is correct, the trial vaccine is received within the labeled storage conditions (i.e., no cold chain break has occurred during transit), and is in good condition. If quantity and conditions are acceptable, investigator or designee will acknowledge receipt of the shipment by recording in IRT.

If there are any discrepancies between the packing list versus the actual product received, the sponsor or designee must be contacted to resolve the issue. The packing list should be filed in the pharmacy investigator site file.

The investigator must maintain 100% accountability for all sponsor-supplied investigational vaccine and placebo doses, and other CTM (including ancillary materials, as applicable) received and administered during their entire participation in the trial. Accountability includes, but is not limited to:

- Verifying that actual inventory matches documented inventory.
- Verifying that the log is completed for the vaccine lot (or investigational vaccine/placebo ID or job number) used to prepare each dose of the trial vaccine.

- Verifying that all kits used are documented accurately on the log.
- Verifying that required fields are completed accurately and legibly.

If any dispensing errors or discrepancies are discovered, the sponsor must be notified immediately.

The investigator must record the current inventory of all sponsor-supplied trial vaccine on a sponsor-approved accountability log. The following information will be recorded at a minimum: protocol number and title, name of investigator, site identifier and number, description of sponsor-supplied trial vaccine, date, and amount. The log should include all required information as a separate entry for each subject to whom sponsor-supplied trial vaccine is administered.

The investigator will be notified of any expiry date or retest date extension of trial vaccine during the trial conduct. On expiry date notification from the sponsor or designee, the site staff must complete all instructions outlined in the notification, including segregation of expired CTM for return to the sponsor or designee for destruction.

All CTM will be provided by the trial site, sponsor or designee, depending upon availability. The list of CTM and source information can be found in the pharmacy manual. Prior to site closure or at appropriate intervals throughout the trial, before any CTM are returned to the sponsor or designee for destruction, a representative from the sponsor will perform CTM accountability and reconciliation. The investigator will retain a copy of the documentation regarding CTM accountability, return, and/or destruction, and originals will be sent to the sponsor or designee.

9.0 TRIAL PLAN

9.1 Trial Procedures

The following sections describe the trial procedures and data to be collected. For each procedure, subjects are to be assessed by the same investigator or site personnel whenever possible. The schedule of procedures is shown in Section 2.3. All procedures must be performed by qualified and trained staff. Details about the trial procedures can be found in the Procedures Manual. All information collected should be recorded in the subject's eCRFs.

9.1.1 Informed Consent Form

The requirements of the ICF are described in Section 15.2.

Informed consent must be obtained before any protocol-directed procedures are performed.

A unique subject number will be assigned to each subject after informed consent is obtained. If all eligibility criteria are fulfilled (Section 7.1 and 7.2), this subject number will be used throughout the trial. Subject numbers assigned to subjects who fail screening should not be reused (Section 9.1.9).

9.1.2 Demographics, Medical History and Prior Medications and Other Vaccinations

Demographic information to be obtained will include age/date of birth (if applicable), sex, race (and ethnicity) as described by the subject's LAR.

Medical history will also be collected, including but not limited to any medical history that may be relevant to subject eligibility for trial participation such as prior vaccinations, concomitant medications and vaccines, and previous and ongoing illnesses and/or injuries. Relevant medical history can also include any medical history that contributes to the understanding of an AE that occurs during trial participation if it represents an exacerbation of an underlying disease/preexisting problem.

Medical history (including corresponding medication) to be obtained will include any significant conditions or diseases that have disappeared or resolved at or prior to signing of the ICF.

Adverse medical occurrences emerging during the time between signing of the ICF and the first administration of the trial vaccine will be recorded in the medical history eCRF page. If such an adverse medical occurrence is assessed as related to a screening procedure this should be recorded as an AE related to trial procedure in the eCRF.

Details of all medications, vaccines and blood products administered or received by the subjects in the following timeframes will be collected as *prior* (prior to Day 1 [Visit 1]), or *concomitant* (from Day 1 [Visit 1] to the time specified up to the end of the trial):

CONFIDENTIAL

- Medications: from 2 months prior to Day 1 (day of first trial vaccine administration), to the time specified up to the end of the trial.
- Vaccines: within 14 days before or after either dose of the trial vaccine, to the time specified up to the end of the trial.
- Blood products: 90 days prior to Day 1 (day of first trial vaccine administration), to the time specified up to the end of the trial.
- Antipyretics and/or analgesic medications within 24 hours prior to trial vaccine administration and the reason for their use (prophylaxis versus treatment) must be documented. Administration of the trial vaccine should be delayed if the subject has received antipyretics within 24 hours prior to trial vaccine administration.

Medications taken for prophylaxis are those intended to prevent the onset of AEs after trial vaccine administration. Medications taken for treatment are intended to reduce or eliminate the presence of symptoms that are present.

These data must be recorded in the source documents.

9.1.3 Documentation of Trial Entry/Randomization

Only subjects for whom there is a signed ICF, and who meet all of the inclusion criteria (Section 7.1) and none of the exclusion criteria (Section 7.2), will be eligible for randomization/entry into the active phase. The randomization schedule will be created by an independent statistician. The randomization specification will be approved by the sponsor's trial statistician, or designee.

If the subject is ineligible for randomization, the investigator should record the primary reason for failure on the subject screening and enrollment log.

9.1.4 Physical Examination

Physical examinations must be performed by a qualified health professional in accordance with local regulations and as listed within the site responsibility delegation log. A physical examination includes but is not limited to the following: a check of general appearance, auscultation of heart and lungs, palpation of the abdomen, and inspection of extremities (including skin over the intended injection site). Weight, length and head circumference will be measured. A complete physical exam will be performed on Day 1, prior to trial vaccine administration, according to the investigator's standard practice. Additional targeted physical examinations may be performed if indicated by review of the subject's medical history. The findings should be documented in the subject's source document.

A symptom-directed physical examination may be performed if deemed necessary.

9.1.5 Vital Signs

During the physical examination, a subject should have their vital signs measured. These will include (but are not limited to), heart rate and body temperature. The investigator will follow standard of care for trial population and operational feasibility.

9.1.6 Immunogenicity Assessments

Subjects in both trial arms will undergo blood sampling for serological immunogenicity testing at the four clinic visits:

- Visit 1 (Day 1; pre-dose 1);
- Visit 2 (Day 28-56; pre-dose 2);
- Visit 3 (28 days post-dose 2);
- Visit 4 (6 months post-dose 2; end-of-trial; unscheduled visit).

All samples must be collected in accordance with acceptable laboratory procedures. The maximum volume of blood taken at any single visit is approximately 3 mL, and the approximate total volume of blood for the trial is maximum 12 mL.

9.1.7 Processing, Labeling and Storage of Biological Samples

All biological samples (e.g., blood and serum) will be processed, labeled, and stored according to the laboratory manual or other appropriate guideline provided to the site (Section 9.4).

9.1.8 Safety Assessments

Safety assessments by site staff are planned immediately following each dose of trial vaccine at Visit 1 and Visit 2, on Day 3 and Day 8 post-dose 1 and dose 2 (phone contacts with the subject's LAR), when subjects return to clinic for dose 2 (Visit 2), 28 days post-dose 2 (Visit 3), and at 6 months post-dose 2 (Visit 4). These assessments will include collection and recording of unsolicited AEs (serious and non-serious) and MAAEs. In addition, the subject's LAR will collect solicited local (injection site) and systemic AEs daily for the 7 days post-dose 1 and dose 2 via the diary card. Refer to Section 10.1 for safety definitions. Details on collection and reporting of AEs are in Section 10.5.

9.1.9 Documentation of Subjects Who Are Not Randomized

Investigators must account for all subjects for whom there is a signed ICF. If the subject is found to be not eligible at this visit, the investigator should complete the eCRF.

The primary reason for non-randomization is recorded in the eCRF using the following categories:

- Screen failure (did not meet one or more inclusion criteria or did meet one or more exclusion criteria).
- Withdrawal by the subject's LAR.
- Withdrawal by the investigator.
- Trial terminated by the sponsor.

Subject numbers assigned to subjects who fail screening should not be re-used.

9.2 Monitoring Subject Compliance

The investigator will record all injections of trial vaccine given to the subject.

9.3 Schedule of Observations and Procedures

The schedule of procedures is shown in Section 2.3. Assessments should be completed at the designated visit(s)/time point(s). In the event that the second dose of trial vaccine is not administered, no blood will be collected at Visit 3 and Visit 4, however these visits should be conducted for safety monitoring at time points relative to the window during which the second dose was to be administered.

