6.0 TRIAL DESIGN AND DESCRIPTION

6.1 Trial Design

This is a phase 1, randomized, double-blind multi-center, placebo-controlled trial in Japan to evaluate the safety and immunogenicity of HIL-214 in healthy infants 5 months of age (-14/+14 days) at first trial vaccine administration. In this protocol, because the trial is blinded, trial vaccine refers to both the investigational vaccine (HIL-214) and placebo.

Subjects (infants - 5 months \pm 14 days) will be allocated (2:1) into 1 of 2 trial arms by interactive response technology (IRT):

- **Arm 1 (N = 14):** One dose of HIL-214 at Visit 1 (Day 1) and one dose of HIL-214 at Visit 2 (Day 29 to Day 57).
- **Arm 2 (N = 7):** One dose of placebo at Visit 1 (Day 1) and one dose of placebo at Visit 2 (Day 29 to Day 57).

The second dose of trial vaccine can be administered from 28 to 56 days after the first dose. Trial vaccine doses will be given at least 14 days before or after all non-live vaccines and oral live vaccines, and at least 28 days before or after parenteral live vaccines.

Trial procedures:

- All subjects will be followed for solicited local and systemic AEs up to 7 days after each dose of trial vaccine and unsolicited AEs up to 28 days after each dose of trial vaccine.
- AEs leading to trial vaccine withdrawal will be collected up to the time of second dose administration (between Day 29 and Day 57).
- All subjects will be followed throughout the trial (from Day 1) for serious adverse events (SAEs), medically-attended AEs (MAAEs), and AEs leading to trial withdrawal.
- All subjects will have four blood draws: pre-dose 1 (Visit 1), pre-dose 2 (Visit 2), 28 days post-dose 2 (Visit 3), and 6 months post-dose 2 (Visit 4), to measure all anti-norovirus total immunoglobulin (pan-Ig) and histoblood group antigen (HBGA) blocking antibodies and conduct exploratory serological immunogenicity testing.
- All subjects will have four safety phone/home contacts (2 and 7 days after each dose).
- All subjects will be followed-up for 6 months after the last dose (Visit 4) for safety.

The trial design diagram is shown in Section 2.2. The schedule of procedures is shown in Section 2.3.

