9.3.6 Final (End of Trial) Visit (Visit 4)

The final (end of trial) visit will be performed at 6 months (Day 180) post-dose 2. Procedures include targeted physical examination, vital signs, and blood draw (~ 3 mL; should be taken from the subject using an aseptic venipuncture technique for serological immunogenicity testing). At Visit 4, the healthcare professional will determine if additional MAAEs or SAEs not already made known to the site occurred after Visit 3, and if concomitant medications and vaccines were used. If a subject terminates earlier, the final (end of trial) visit procedures should be performed at their last trial visit, if possible. The investigator must complete the End of Trial eCRF page for all subjects who received the trial vaccine.

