## 4. General Statistical Considerations

Continuous data will be analyzed using descriptive statistics (i.e. n, geometric or arithmetic mean, standard deviation, median, minimum, maximum, first quartile (Q1), third quartile (Q3) and 95% confidence intervals [where applicable]). Categorical data will be analyzed using the subject count and percentage in each category. For the summary statistics of all numerical

variables unless otherwise specified, minimum and maximum will be displayed to the same level of precision as reported. Mean, median, Q1 and Q3 will be displayed to one level of precision greater than the data collected. Standard deviation will be displayed to two levels of precision greater than the data collected. Any results that are below the lower limit of quantification (LLOQ) and above the limit of detection (LOD) will be imputed as the middle point between the LOD and the LLOQ. Any results below the LOD will be imputed as half the LOD. Results above the upper limit of quantification (ULOQ) will be imputed as that limit for analysis purposes.

When count data are presented, the percentage will be suppressed when the count is zero in order to draw attention to the non-zero counts. A row denoted “Missing” will be included in count tabulations where specified on the shells to account for dropouts and missing values. The denominator for all percentages will be the number of subjects in that trial arm within the analysis set of interest, unless otherwise specified.

Unless otherwise specified, baseline will be defined as the last non-missing evaluation taken before dose 1 including both scheduled and unscheduled visits. The study day will be calculated relative to dose 1:

- If assessment date is on or after the date of dose 1 then Study Day = Assessment Date – Dose 1 Date + 1.
- Otherwise, Study Day = Assessment Date – Dose 1 Date

All analyses will be conducted using SAS Version 9.4 or higher.

Unless otherwise specified (i.e., baseline) data will be summarized based on the visit name collected on the case report form (CRF) page and presented by trial arm and overall. Unscheduled visit measurements will be included in the derivation of baseline for safety analyses and included in individual subject data listings as appropriate.

95% confidence intervals (CIs) are provided as 2-sided and by displaying the lower limit and upper limit as follows (XX.X, XX.X).

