#### **4.1. Sample Size**

A total of 21 subjects is planned to be enrolled in order to achieve enrolment of 14 subjects in the HIL-214 arm and 7 subjects in the Placebo arm.

The objective of this trial is to evaluate the safety and immunogenicity of two IM injections of HIL-214 in infants aged 5 months ( $\pm 14$  days) at first trial vaccine administration. This trial is designed to be descriptive, and therefore the sample size was not determined based on formal statistical power calculations.

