## 8. Immunogenicity Analysis

All subjects will have four blood draws: pre-dose 1 (Visit 1 - Baseline), pre-dose 2 (Visit 2), 28 days post-dose 2 (Visit 3), and 6 months post-dose 2 (Visit 4), to measure all anti-norovirus total immunoglobulin (Pan-Ig) and histoblood group antigen (HBGA) blocking antibodies. Unless otherwise stated the immunogenicity analyses will be performed using the PPS. All immunogenicity data will be listed for the FAS. See section 3.2 for a list of the immunogenicity endpoints and summary measures.

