### 8.1. Immunogenicity Endpoints

The following evaluations will be performed on the Pan-Ig and HBGA assays:

- Geometric mean titer (GMT) with 95% CI, geometric SD, minimum, maximum, Q1 and Q3. at baseline (Visit 1), Visit 2 (pre-dose 2), Visit 3 (28 days post-dose 2) and Visit 4 (6 months post-dose 2). The 95% CI will be calculated based on the t distribution of the log-transformed values for GMTs, then back transformed to the original scale for presentation.
- Geometric mean fold rise (GMFR) with 95% CI at Visit 2 (pre-dose 2), Visit 3 (28 days post-dose 2) and Visit 4 (6 months post-dose 2) relative to baseline. The 95% CI will be calculated based on the t distribution of the log-transformed values for GMFRs, then back transformed to the original scale for presentation.
- Seroresponse rate (SRR) with 95% CI based on the exact Clopper-Pearson method. Seroresponse is defined as a  $\geq 4$ -fold increase at Visit 2 (pre-dose 2), Visit 3 (28 days post-dose 2) and Visit 4 (6 months post-dose 2) relative to baseline, all considered separately. SRR of GI.1, GII.4 and GI.1 and GII.4 will be analyzed.

The GMT will be calculated using the following formula:

$$10^{\left\{ \frac{\sum_{i=1}^n \log_{10}(t_i)}{n} \right\}}$$

where  $t_1, t_2, \dots, t_n$  are observed immunogenicity titers for  $n$  subjects.

The GMFR measures the changes in immunogenicity titers within subjects. The GMFR will be calculated using the following formula:

$$10^{\left\{ \frac{\sum_{i=1}^n \log_{10} \frac{v_{ij}}{v_{ik}}}{n} \right\}} = 10^{\left\{ \frac{\sum_{i=1}^n (\log_{10} v_{ij} - \log_{10} v_{ik})}{n} \right\}}$$

where, for  $n$  subjects,  $v_{ij}$  and  $v_{ik}$  are observed immunogenicity titers for subject  $i$  at time points  $j$  and  $k = 0$  (Baseline).

Boxplots of titer and fold rise for the pan-Ig and HBGA assays will be plotted. Reverse cumulative distribution curves for the pan-Ig and HBGA assays will also be plotted.

All endpoints will be summarized by both the PPS and FAS.

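### SAP 8.1 sets no denominator for the seroresponse rate, so FAS infants who miss dose 2 and are not bled afterwards still count in it and pull the rate down

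*Protocol*

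**What the plan says.** **Who is bled.** Protocol 6.1 states the schedule without exception: "All subjects will have four blood draws: pre-dose 1 (Visit 1), pre-dose 2 (Visit 2), 28 days post-dose 2 (Visit 3" and then Visit 4. SAP 8 repeats it: "All subjects will have four blood draws: pre-dose 1 (Visit 1 - Baseline), pre-dose 2 (Visit 2", followed by Visits 3 and 4. Protocol 9.3 deals with the infant who does not get dose 2: "no blood will be collected at Visit 3 and Visit 4, however these visits should be conducted for safety monitoring". The SAP does not mention this exception. For infants who leave early, Protocol 9.3.6 adds: "If a subject terminates earlier, the final (end of trial) visit procedures should be performed at their last trial visit, if possible". The final-visit procedures include a blood draw.

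**Who is analysed.** The FAS keeps every randomized infant with at least one dose (SAP 4.3.2). The PPS excludes incomplete vaccination as a major deviation (SAP 5.2) and is the primary immunogenicity set (SAP 4.3.3). Protocol 7.5 allows an infant to stop vaccination and stay in follow-up, so infants in the FAS without dose 2 are foreseen. On immunogenicity, SAP 8.1 says: "All endpoints will be summarized by both the PPS and FAS".

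**How the rates are formed.** SAP 8.1 computes GMT and GMFR from observed titers. For SRR it gives the 4-fold definition and the Clopper-Pearson method, but no denominator. SAP 4 fills the gap: the "denominator for all percentages will be the number of subjects in that trial arm within the analysis set of interest", unless something else is specified.

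**The concern.** At Visits 3 and 4, an infant without dose 2 has no titer because the protocol says not to take one. GMT and GMFR leave that infant out. The SRR keeps the infant in the denominator, where a response can never be recorded. FAS GMFR and FAS SRR at the same visit would then describe different groups of infants, and the SRR would be lowered by absent samples instead of by absent responses.

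The same default reaches any infant with a failed or missing draw, in the PPS as well as the FAS.

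There is also a risk of misreading. A reader may take the FAS tables as showing what happens when infants excluded from the PPS for a missed second dose are put back. After dose 2 they cannot show that, because those infants have no titers.

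**Working it through.** **Inputs**
- Arm sizes (SAP 4.1): "14 subjects in the HIL-214 arm and 7 subjects in the Placebo arm". Subjects randomized but not dosed are replaced (SAP 4.2), so these are also the planned FAS sizes.
- SRR denominator: the SAP 4 default, because SAP 8.1 gives no other. Where the SAP wants a different base it says so: SAP 9.1 bases solicited-AE percentages on subjects with data for that category and day. SRR has no such wording.
- Rate of missed second doses: not given in the documents. Assumed here as 0 to 3 infants per arm, or 5% to 20% per infant.

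There is no plan figure to reproduce, since the "sample size was not determined based on formal statistical power calculations".

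**Formula.** Let N be the FAS size of the arm, m the infants without a usable titer at the visit, n = N − m the infants with baseline and visit titers, and x the responders.
- SRR among infants with titers: x/n
- SRR under the SAP default: x/N
- Difference: x/n − x/N = (x/n) × (m/N), which is at most m/N

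For m = 1 the maximum is 1/14 = 7.1 points on HIL-214 and 1/7 = 14.3 points on placebo. The loss is proportional to the response rate, so it disappears in an arm with no responders.

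**Illustrations** (exact Clopper-Pearson 95% intervals)

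| Arm, assumed m | Responders | x/n | x/N (SAP default) | Difference, points |
|---|---|---|---|---|
| HIL-214, 1 | 13 of 13 | 100% (75.3–100) | 13/14 = 92.9% (66.1–99.8) | 7.1 |
| HIL-214, 2 | 12 of 12 | 100% (73.5–100) | 12/14 = 85.7% (57.2–98.2) | 14.3 |
| HIL-214, 2 | 10 of 12 | 83.3% (51.6–97.9) | 10/14 = 71.4% (41.9–91.6) | 11.9 |
| HIL-214, 3 | 11 of 11 | 100% (71.5–100) | 11/14 = 78.6% (49.2–95.3) | 21.4 |
| Placebo, 1 | 5 of 6 | 83.3% (35.9–99.6) | 5/7 = 71.4% (29.0–96.3) | 11.9 |

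Check of the third row: 0.833 × 2/14 = 0.119. The placebo row is arithmetic only, not a forecast of placebo response.

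**How likely is at least one case?** With an independent chance d of missing dose 2, the probability of at least one such infant among 21 is 1 − (1 − d)^21. This gives 66% for d = 5%, 89% for d = 10% and 99% for d = 20%.

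**The case against.** **The protocol sections can be read as rule and exception.** Section 6.1 gives the planned schedule, and its last two draws are timed from dose 2. Section 9.3 covers the infant for whom those times do not exist. This stands: a reader might infer a flat contradiction over blood sampling, but 6.1 and 9.3 can be read together. What remains is that the SAP does not carry the exception and that 9.3.6 is not tied to it. On one reading of 9.3.6, an infant without dose 2 who leaves early is bled while one who stays is not. That is an inference, not a stated rule: 9.3.6 says only if possible, sits within Section 9.3, and a last visit at Visit 2 already has its own draw.

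**No rule scores unsampled infants as failures.** This also stands. A reader might infer a non-responder rule, but the SAP has none. SAP 4 bars imputation beyond what it specifies, and it allows a row for missing values where the table shells call for one. The shells are not among the documents reviewed. The lower SRR is an arithmetic result of the default denominator, which is enough to make it misleading.

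**The FAS is not empty of PPS exclusions.** Correct. Infants outside the PPS for other deviations who received two doses are bled at Visits 3 and 4, and infants without dose 2 can still contribute Visit 1 and Visit 2 titers.

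**The stakes are limited.** The trial is descriptive, the primary objective is safety, the PPS leads for immunogenicity, and Protocol 13.1.3 makes FAS analyses optional. No test or decision rule uses the FAS SRR, and the compared intervals overlap widely. All of this bears on the weight of the point, not on whether the denominator should be stated.

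**Conclusion.** The point holds as a defect in the SRR denominator. As written, the SAP keeps infants without a titer in the denominator while GMT and GMFR leave them out. The maximum effect of 7.1 or 14.3 points per infant rests on the planned arm sizes and on every sampled infant responding. The 71.4% against 83.3% example rests on assumed counts. If every infant has baseline and visit titers, the effect is zero.

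The primary safety objective is not affected, nor is the PPS exclusion for incomplete vaccine. The PPS SRR is exposed only through a missing titer in an infant it retains.

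A reader might also infer that the missing samples will fall unevenly by arm, for example through more stopping for adverse events on HIL-214. The documents give no figure for this, and Protocol 7.5 lists several other reasons for stopping, so no such claim is made here.

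**What to change.** 1. In SAP 8.1, set the SRR denominator, for both PPS and FAS, to infants with a baseline titer and a titer at the visit concerned. This is the same n as GMFR. Print that n in every SRR table.
2. In SAP 8, state the Protocol 9.3 exception to the four-draw schedule. Label the Visit 3 and Visit 4 FAS summaries as covering sampled infants, so that they are not read as a check on PPS exclusions for a missed second dose.
3. Reconcile Protocol 6.1, 9.3 and 9.3.6 so that one statement says who is bled at Visits 3 and 4. Which rule applies is for the sponsor to decide. If infants without dose 2 are to be sampled, the SAP must also say how their titers are labelled, because both visits are named by time since dose 2.

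Items 1 and 2 cost SAP wording and table labels, with no new data. Item 3 costs a protocol clarification. Should it add draws for infants without dose 2, those fit within the stated maximum (4 draws × about 3 mL = 12 mL).
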